### **5.2.2 Dose Modification and toxicity management for immune-related AEs associated with pembrolizumab**

AEs associated with pembrolizumab exposure, including coadministration with additional compounds, may represent an immunologic etiology. These immune-related AEs (irAEs) may occur shortly after the first dose or several months after the last dose of pembrolizumab/combination treatment and may affect more than one body system simultaneously. Therefore, early recognition and initiation of treatment are critical to reduce complications. Based on existing clinical study data, most irAEs were reversible and could be managed with interruptions of pembrolizumab//combination treatment, administration of corticosteroids and/or other supportive care. For suspected irAEs, ensure adequate evaluation to confirm etiology or exclude other causes. Additional procedures or tests such as bronchoscopy, endoscopy, skin biopsy may be included as part of the evaluation. Based on the severity of irAEs, withhold or permanently discontinue pembrolizumab and administer corticosteroids. Dose modification and toxicity management guidelines for irAEs associated with pembrolizumab/combination treatment are provided in Table 5.4.

#### **Attribution of Toxicity:**

When study interventions are administered in combination, attribution of an adverse event to a single component is likely to be difficult. Therefore, while the investigator may attribute a toxicity event to the combination, to Vorinostat or Tamoxifen alone, or to pembrolizumab alone, for adverse events listed in Table 5.4, both interventions must be held according to the criteria in Table 5.4 Dose Modification and Toxicity Management Guidelines for Immune-Related Adverse Events Associated with Pembrolizumab.

#### **Holding Study Interventions:**

When study interventions are administered in combination, if the AE is considered immune-related, both interventions should be held according to recommended dose modifications.

#### **Restarting Study Interventions:**

Participants may not have any dose modifications (no change in dose or schedule) of pembrolizumab in this study, as described in Table 5.4.

- If the toxicity does not resolve or the criteria for resuming treatment are not met, the participant must be discontinued from all study interventions.
- If the toxicities do resolve and conditions are aligned with what is defined in Table 5.4, the combination of Vorinostat, Tamoxifen and pembrolizumab may be restarted at the discretion of the investigator. In these cases where the toxicity is attributed to the combination or to Vorinostat or Tamoxifen alone, re-initiation of pembrolizumab as a monotherapy may be considered at the PI's discretion.

**Table 5.4 Dose modification and toxicity management guidelines for immune-related AEs associated with pembrolizumab monotherapy and IO Combinations**

irAEs	Toxicity Grade (CTCAE v5.0)	Action With Pembrolizumab	Corticosteroid and/or Other Therapies	Monitoring and Follow-up
Pneumonitis	Grade 2	Withhold	
 
• Administer corticosteroids (initial dose of 1 to 2 mg/kg prednisone or equivalent) followed by taper
 
• Add prophylactic antibiotics for opportunistic infections
 
	
 
• Monitor participants for signs and symptoms of pneumonitis
 
• Evaluate participants with suspected pneumonitis with radiographic imaging and initiate corticosteroid treatment
 

	Recurrent Grade 2, Grade 3 or 4	Permanently discontinue		
Diarrhea/Colitis	Grade 2 or 3	Withhold	
 
• Administer corticosteroids (initial dose of 1 to 2 mg/kg prednisone or equivalent) followed by taper
 
	
 
• Monitor participants for signs and symptoms of enterocolitis (ie, diarrhea, abdominal pain, blood or mucus in stool with or without fever) and of bowel perforation (ie, peritoneal signs and ileus)
 
• Participants with ≥Grade 2 diarrhea suspecting colitis should consider GI consultation and performing endoscopy to rule out colitis
 
• Participants with diarrhea/colitis should be advised to drink liberal quantities of clear fluids. If sufficient oral fluid intake is not feasible, fluid and electrolytes should be
 

	Recurrent Grade 3 or Grade 4	Permanently discontinue		

irAEs	Toxicity Grade (CTCAE v5.0)	Action With Pembrolizumab	Corticosteroid and/or Other Therapies	Monitoring and Follow-up
				substituted via IV infusion
AST or ALT Elevation or Increased Bilirubin	Grade 2 a	Withhold	
 
Administer corticosteroids (initial dose of 0.5 to 1 mg/kg prednisone or equivalent) followed by taper
 
	
 
Monitor with liver function tests (consider weekly or more frequently until liver enzyme value returned to baseline or is stable)
 

	Grade 3 b or 4 c	Permanently discontinue	
 
Administer corticosteroids (initial dose of 1 to 2 mg/kg prednisone or equivalent) followed by taper
 
	
T1DM or Hyperglycemia	New onset T1DM or Grade 3 or 4 hyperglycemia associated with evidence of $\beta$ -cell failure	Withhold d	
 
Initiate insulin replacement therapy for participants with T1DM
 
Administer antihyperglycemic in participants with hyperglycemia
 
	
 
Monitor participants for hyperglycemia or other signs and symptoms of diabetes
 

Hypophysitis	Grade 2	Withhold	
 
Administer corticosteroids and initiate hormonal replacements as clinically indicated
 
	
 
Monitor for signs and symptoms of hypophysitis (including hypopituitarism and adrenal insufficiency)
 

	Grade 3 or 4	Withhold or permanently discontinue d		

irAEs	Toxicity Grade (CTCAE v5.0)	Action With Pembrolizumab	Corticosteroid and/or Other Therapies	Monitoring and Follow-up
Hyperthyroidism	Grade 2	Continue	
 
Treat with nonselective beta-blockers (eg, propranolol) or thionamides as appropriate
 
	
 
Monitor for signs and symptoms of thyroid disorders
 

	Grade 3 or 4	Withhold or permanently discontinue d		
Hypothyroidism	Grade 2, 3 or 4	Continue	
 
Initiate thyroid replacement hormones (eg, levothyroxine or liothyronine) per standard of care
 
	
 
Monitor for signs and symptoms of thyroid disorders
 

Nephritis: grading according to increased creatinine or acute kidney injury	Grade 2	Withhold	
 
Administer corticosteroids (prednisone 1 to 2 mg/kg or equivalent) followed by taper
 
	
 
Monitor changes of renal function
 

	Grade 3 or 4	Permanently discontinue		
Neurological Toxicities	Grade 2	Withhold	
 
Based on severity of AE administer corticosteroids
 
	
 
Ensure adequate evaluation to confirm etiology and/or exclude other causes
 

	Grade 3 or 4	Permanently discontinue		
Myocarditis	Grade 1	Withhold	
 
Based on severity of AE administer corticosteroids
 
	
 
Ensure adequate evaluation to confirm etiology and/or exclude other causes
 

	Grade 2, 3 or 4	Permanently discontinue		
Exfoliative Dermatologic Conditions	Suspected SJS, TEN, or DRESS	Withhold	
 
Based on severity of AE administer
 
	
 
Ensure adequate evaluation to confirm etiology
 

irAEs	Toxicity Grade (CTCAE v5.0)	Action With Pembrolizumab	Corticosteroid and/or Other Therapies	Monitoring and Follow-up
	Confirmed SJS, TEN, or DRESS	Permanently discontinue	corticosteroids	or exclude other causes
All Other irAEs	Persistent Grade 2	Withhold	
 
Based on severity of AE administer corticosteroids
 
	
 
Ensure adequate evaluation to confirm etiology or exclude other causes
 

	Grade 3	Withhold or discontinue based on the event e		
	Recurrent Grade 3 or Grade 4	Permanently discontinue		

AE(s)=adverse event(s); ALT= alanine aminotransferase; AST=aspartate aminotransferase; CTCAE=Common Terminology Criteria for Adverse Events; DRESS=Drug Rash with Eosinophilia and Systemic Symptom; GI=gastrointestinal; IO=immuno-oncology; ir=immune related; IV=intravenous; SJS=Stevens-Johnson Syndrome; T1DM=type 1 diabetes mellitus; TEN=Toxic Epidermal Necrolysis; ULN=upper limit of normal.

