## 3 Study Design

### 3.1 Characteristics

We propose a single site Phase II, two-arm, open-label unblinded, 65-patient trial in patients with hormone therapy-resistant breast cancer (HTR) to test the role of epigenetic priming in a biomarker enriched patient population in HTR breast cancer. The two arms include Arm A: pembrolizumab, vorinostat, and tamoxifen and Arm B pembrolizumab and tamoxifen.

Patients will be evaluated for response at 9 weeks ( $\pm 1$  week) by RECIST1.1 (using IR-RECIST) and will continue on therapy if they have stable disease or response at the time of disease evaluations. Patients with progression on imaging but are clinically stable, may stay on study but will require follow-up staging after 4-6 weeks. Patients will be assessed continually for safety and tolerability as well as for any adverse events. If progression on therapy with pembrolizumab, patient may continue if clinically indicated and be re-evaluated after 4-8 weeks.

We will follow AEs of clinical interest as defined by Merck and will dose modify pembrolizumab as per Merck guidelines. We have significant prior experience with vorinostat, tamoxifen, and pembrolizumab combination and are facile with managing drug toxicities.

Tissue biopsies of all patients will be collected prior to enrollment to assess for pre-treatment of our immune signature and PD-L-1 expression. Follow up biopsies and peripheral blood collection will be taken from all patients post-treatment at 8-10 weeks to characterize changes in local tissue effects and antigen-specific cellular and humoral immune responses in peripheral blood.

Patients will be stratified by prior number of hormonal and chemotherapies.

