## **5 Treatment Plan**

### **5.1 Dosage and Administration**

All trial treatments will be administered on an outpatient basis.

Pembrolizumab 200 mg will be administered as a 30-minute IV infusion every 3 weeks. Treatment cycle intervals may be increased due to toxicity, as described in Section 5.2. Every effort should be made to target infusion timing to be as close to 30 minutes as possible. However, given the variability of infusion pumps, a window of -5 minutes and +10 minutes is permitted (i.e., infusion time is 30 minutes: -5 min/+10 min).

The Pharmacy Manual contains specific instructions for the preparation of the pembrolizumab infusion fluid and administration of infusion solution.

Selection of 200 mg as the appropriate dose for a switch to fixed dosing is based on simulation results indicating that 200 mg will provide exposures that are reasonably consistent with those obtained with 2 mg/kg dose and importantly will maintain individual patient exposures within the exposure range established in melanoma as associated with maximal clinical response. A population PK model, which characterized the influence of body weight and other patient covariates on exposure, has been developed using available data from 476 subjects from PN001. The distribution of exposures from the 200 mg fixed dose is predicted to considerably overlap those obtained with the 2 mg/kg dose, with some tendency for individual values to range slightly higher with the 200 mg fixed dose. The slight increase in PK variability predicted for the fixed-dose relative to weight-based dosing is not expected to be clinically important given that the range of individual exposures is well contained within the range of exposures shown in the melanoma studies of 2 and 10 mg/kg to provide similar efficacy and safety. The population PK evaluation revealed that there was no significant impact of tumor burden on exposure. In addition, exposure was similar between the NSCLC and melanoma indications. Therefore, there are no anticipated changes in exposure between different tumor types and indication settings. As vorinostat and tamoxifen are oral, self-administered drugs, drug diaries will be provided for assessing compliance with treatment. The diary will be provided each time vorinostat and tamoxifen are provided to the study participant to take home. Missed doses will be noted and will not be replaced. The participant will proceed with the next scheduled dose at the next scheduled time.

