## 5.2 Dose Modifications and Dosing Delays

The following dose modification rules will be used with respect to potential toxicity. Toxicity will be assessed according to the NCI CTCAE version 5.0.

The following dose modifications should be made for febrile neutropenia, and blood counts obtained on day one of each cycle. If more than one of these conditions applies, use the most stringent (i.e., the greatest dose reduction). **The AE may be due to pembrolizumab or vorinostat alone in which case the respective agent should be reduced. If overlapping toxicity is suspected, both drugs may be reduced with the potential to re-escalate the non-offending agent. Given the very different nature of pembrolizumab and vorinostat/tamoxifen toxicities, separate tables are shown for individual agents.**

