**Gastrointestinal Toxicity**

**Nausea/Vomiting/Dehydration:** In this protocol, the routine use of any and all anti-emetics is allowed as clinically appropriate; these include the use of dexamethasone and 5-HT3 receptor antagonists.

Patients should maintain adequate fluid and food intake because vorinostat's dose-limiting toxicities are anorexia, dehydration, diarrhea, and fatigue. In the setting of dysgeusia, popsicles and Gatorade have been found to be useful by some investigators to maintain adequate hydration. Patients should also be encouraged to seek a nutritional consult.

**Diarrhea:** Treat diarrhea promptly with appropriate supportive care, including loperamide. Instruct patients to begin taking loperamide at the first signs of 1) poorly formed or loose stool, 2) occurrence of more bowel movements than usual in one day, or 3) unusually high volume of stool. Loperamide should be taken in the following manner: 4 mg at first onset of diarrhea then 2 mg after each unformed stool. The daily dose should not exceed 16 mg. Loperamide should not be taken prophylactically. Advise patients to drink plenty of clear fluids to help prevent dehydration caused by diarrhea. Avoid loperamide if there is the presence of blood or mucus in the stool or if diarrhea is accompanied by fever. If diarrhea is suspected to be linked to pembrolizumab and is ≥ grade 3, hold dose until toxicity resolves to ≤ grade 1, then resume at dose given in prior cycle.

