**Table 5.6 Recommended Approach to Handling Pneumonitis**

Study drug associated pneumonitis	Withhold/Discontinue pembrolizumab	Supportive Care
Grade 1 (asymptomatic)	No action	Intervention not indicated
Grade 2	Withhold pembrolizumab, may return to treatment if improves to Grade 1 or resolves within 12 weeks	Systemic corticosteroids are indicated. Taper if necessary.
Grade 3 and Grade 4	Discontinue pembrolizumab	Systemic corticosteroids are indicated. The use of infliximab may be indicated as appropriate. Refer to the Event of Clinical Interest and Immune-related Adverse Event Guidance Document for additional recommendations.

For Grade 2 pneumonitis that improves to  $\leq$  Grade 1 within 12 weeks, the following rules should apply:

- First episode of pneumonitis
  - May increase dosing interval by one week in subsequent cycles
- Second episode of pneumonitis – permanently discontinue pembrolizumab if upon rechallenge subject develops pneumonitis  $\geq$  Grade 2

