## 8.2 Interim Analyses and Stopping Rules

This is a randomized two-arm trial with futility early stopping built-in within each treatment arm using a Simon's two-stage design.

In addition to the interim analysis for efficacy that is built into the Simon 2-stage design (see above), in each arm, we will evaluate the need for dose modification after 6 patients have been enrolled. If 2 or more patients have a grade 3 non-hematologic toxicity that is clearly related to pembrolizumab, this agent will be reduced to 75%. Dose modification of vorinostat should be undertaken as per dose modification guidelines, a prior study with vorinostat and tamoxifen suggest that there is a high interpatient variability and tolerance and vorinostat will be adjusted per dose modification guidelines individually.

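### Section 8.2 orders a cut of pembrolizumab to 75% when an arm's toxicity trigger fires, but Section 5.2.2 bars any change in its dose or schedule; patients already on 200 mg can fall under both rules

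*Combined protocol and SAP*

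**What the plan says.** Section 8.2 adds a toxicity look to the Simon futility stages. After 6 patients are enrolled in an arm, the need for dose modification is evaluated. If 2 or more "have a grade 3 non-hematologic toxicity that is clearly related to pembrolizumab, this agent will be reduced to 75" per cent. It does not say whether the cut covers patients already on treatment, patients enrolled later, or both.

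Section 5.2.2, in the paragraph on restarting study interventions, says: "Participants may not have any dose modifications (no change in dose or schedule) of pembrolizumab in this study, as described in Table 5.4". Table 5.4 gives only continue, withhold or permanently discontinue. Tables 5.1 to 5.3 list 200 mg and no other pembrolizumab dose.

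Other current text also bears on pembrolizumab dose or interval:

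- Section 3.1: "will dose modify pembrolizumab as per Merck guidelines".
- Section 5.1: "Treatment cycle intervals may be increased due to toxicity, as described in Section 5.2".
- Section 5.2, opening text: "The AE may be due to pembrolizumab or vorinostat alone in which case the respective agent should be reduced".
- Section 5.2, diarrhea of grade 3 or higher linked to pembrolizumab: "hold dose until toxicity resolves to ≤ grade 1, then resume at dose given in prior cycle".
- Table 5.6, after a first grade 2 pneumonitis: "May increase dosing interval by one week in subsequent cycles".

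No text gives either rule precedence or exempts one from the other.

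**The concern.** Both rules are mandatory and concern the same drug. If the trigger fires, giving 150 mg to a patient who started on 200 mg breaches the words of Section 5.2.2, and giving 200 mg breaches Section 8.2.

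Section 8.2 is the only arm-level toxicity rule with a stated count. The termination criteria in Section 5.3 give no number, and Appendix 2 compares grade 3 or 4 event rates with those in the Investigator Brochure or package insert. The rule should therefore be executable as written.

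The trigger also names grade 3 alone. Taken literally, two clearly related grade 4 toxicities among six patients would not fire it.

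**Working it through.** The plan states no operating characteristic for this trigger, so there is no figure to reproduce. The check is mainly a comparison of texts.

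**Reduced dose.** 0.75 × 200 mg = 150 mg, a level that none of the regimen tables contains.

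**Who falls under both rules.** The ban in Section 5.2.2 can be read widely (every participant, throughout the study) or narrowly (only restarts after the immune-related events of Table 5.4).

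| Patient when the trigger fires | Section 8.2 | Wide reading of 5.2.2 | Narrow reading of 5.2.2 |
|---|---|---|---|
| On 200 mg, restarting after an immune-related event | 150 mg | contradiction | contradiction |
| On 200 mg, no immune-related hold | 150 mg | contradiction | no clash |
| Enrolled after the cut | scope not stated | unclear | unclear |

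The first row is a contradiction on either reading because the Section 8.2 trigger is not confined to non-immune toxicity. For example, Table 5.4 withholds for a first grade 3 diarrhea or colitis. If clearly related to pembrolizumab, that event counts toward the trigger, and the same patient may later restart under Section 5.2.2.

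The third row is unclear rather than contradictory. Section 5.2.2 restricts changes for a participant and names no dose, so a patient who starts at 150 mg has had no change. Tables 5.1 to 5.3 still show only 200 mg.

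The diarrhea instruction in Section 5.2 adds little. It conflicts with Section 8.2 only for a patient held for diarrhea whose last dose predates the cut. Once a patient is on 150 mg, the prior-cycle dose is 150 mg.

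**How many.** At the look, at most 6 patients per arm, so at most 2 × 6 = 12 if both arms trigger, plus any enrolled before the cut takes effect. In practice there would be fewer: Table 5.4 permanently discontinues grade 3 pneumonitis, hepatic, renal and neurological events, so some triggering patients would be off pembrolizumab.

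**How often.** With X the number of qualifying patients among 6 and p the assumed true rate,

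P(X ≥ 2) = 1 − (1 − p)^6 − 6p(1 − p)^5.

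At p = 0.06: 1 − 0.6899 − 0.2642 = 0.0459.

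| Assumed p | Chance of firing, one arm |
|---|---|
| 3% | 1.2% |
| 6% | 4.6% |
| 12% | 15.6% |
| 20% | 34.5% |
| 30% | 58.0% |

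These rates are assumptions. The pilot in Section 1.3.1.2 cannot supply p. It reports grade 3-4 events (2 of 34 for each type) on the triple combination without attribution to pembrolizumab, and 6 of the 34 patients never received pembrolizumab.

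**Efficacy design.** Exact two-stage binomial calculation gives alpha 0.0249 and power 0.904 for Arm A, and 0.0220 and 0.900 for Arm B, in line with the stated 0.025 and 0.9. These depend on the response cut-offs, stage sizes and assumed response rates, none of which this conflict alters.

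**The case against.** The strongest reply is that Section 5.2.2 is not a trial-wide ban. The sentence stands under a restart heading, is tied to Table 5.4 and is followed by bullets on resuming after toxicity. The note after that table leaves non-immune events to clinical practice. Sections 3.1, 5.1, 5.2, 8.2 and Table 5.6 all contemplate a change in pembrolizumab dose or interval, so the restart sentence looks like the outlier.

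Much of this stands. A reader might infer that every later patient in a triggered arm faces contradictory doses. The documents do not support that, because Section 5.2.2 names no 200 mg dose. The narrow reading still leaves the restart case. Confining the cut to later patients would remove that case too, but Section 8.2 contains no such limit.

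A reader might also infer that the cut should simply be deleted, since Section 5.1 places the fixed dose within the "range of exposures shown in the melanoma studies of 2 and 10 mg/kg to provide similar efficacy and safety". That text supports choosing 200 mg. It does not address reducing the dose in an arm after observed toxicity, so the choice remains the sponsor's.

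Finally, it is fair to say that individual toxicities keep their own management and review. Table 5.4 covers grade 4 immune-related events, and Appendix 2 has grade 3-5 events reviewed monthly. The general grade 4 row under Other Non-hematological Toxicities in Section 5.2 should not be counted here: it belongs to a vorinostat dosing table and gives no cover for pembrolizumab or for Arm B.

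**Conclusion.** The conflict is real and should be fixed, within limits. It is firm for patients already on 200 mg who restart after an immune-related event, and wider if Section 5.2.2 is taken at its literal word. It reaches at most 6 patients per arm at the look, plus any enrolled before the cut takes effect, and only if the trigger fires. For later patients the defect is an unstated scope. The omission of grade 4 is a literal reading and is limited to the arm-level count; it does not mean that grade 4 events go unmanaged.

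The frequency range of about 1% to 58% per arm rests wholly on assumed true rates of 3% to 30%. A reader might infer some damage to the efficacy test, but alpha, power and sample size are unaffected. The differing instructions for grade 3 enterocolitis (Sections 5.2.1 and 6.5.2 against Table 5.4) do not involve Section 8.2 and are a separate point.

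**What to change.** In Section 8.2, change the trigger to grade 3 or higher. Then take one of two routes, at the sponsor's choice:

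1. Replace the 75% cut with DSMC review of that arm, leaving individual dosing to Table 5.4.
2. Keep the cut and state whether it covers continuing patients, later patients or both. Either name it in Section 5.2.2 as an exception, or limit the Section 5.2.2 sentence to restarts after immune-related events. If the sentence is limited in that way, state which dose applies to a patient who restarts after the cut.

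In the same amendment, align the interval wording in Section 5.1, the reduction wording in Section 5.2 and the pneumonitis interval extension in Table 5.6 with the chosen rule.

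The cost is a wording amendment through the usual approvals (Section 9.4), with no added visits, procedures or patients. Route 1 uses a committee that already meets every six weeks (Section 7.3.6).
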